3.4.4 Withdrawal of patients from therapy or assessments

Patients may potentially be withdrawn from trial treatment or from the trial as a whole (“withdrawal of consent”) with very different implications, please see sections 3.4.4.1 and 3.4.4.2 below.

Every effort should be made to keep the randomised patients in the trial: if possible on treatment, or at least to collect important trial data.

Measures to control the withdrawal rate include careful patient selection, appropriate explanation of the trial requirements and procedures prior to randomization, as well as the explanation of the consequences of withdrawal.

The decision to withdraw from trial treatment or from the whole trial as well as the reason must be documented in the patient files and Case Report Form (CRF).

3.4.4.1 Withdrawal from trial treatment

An individual patient is to be withdrawn from trial treatment if:

- The patient wants to withdraw from trial treatment, without the need to justify the decision.
- The patient needs to take concomitant drugs that interfere with the investigational product or other trial medication.
- The patient can no longer be treated with trial medication for other medical reasons (such as surgery, adverse events, other diseases, or pregnancy).
- The patient has repeatedly shown to be non-compliant with important trial procedures and, in the opinion of both, the investigator and sponsor representative, is not willing or able to stick to the trial requirements in the future.

Given the patient’s agreement, the patient will undergo the procedures for early treatment discontinuation and follow up as outlined in the [Flow Chart](#) (FC) and [section 6.2.2](#) and [section 6.2.3](#). For all patients the reason for withdrawal from trial treatment (e.g. adverse events) must be recorded in the CRF. These data will be included in the trial database and reported.

3.4.4.2 Withdrawal of consent for trial participation

Patients may withdraw their consent for trial participation at any time without the need to justify the decision.

This will however mean that no further information may be collected for the purpose of the trial and negative implications for the scientific value may be the consequence. Furthermore it may mean that further patient follow up on safety cannot occur.

If a patient wants to withdraw consent, the investigator should explain the difference between treatment withdrawal and withdrawal of consent for trial participation and explain the options for continued follow up after withdrawal from trial treatment, please see section 3.4.4.1 above.

3.4.4.3 Discontinuation of the trial by the sponsor

Boehringer Ingelheim reserves the right to discontinue the trial overall or at a particular trial site at any time for the following reasons:

1. Failure to meet expected enrollment goals overall or at a particular trial site
2. Emergence of any efficacy/safety information invalidating the earlier positive benefit-risk-assessment that could significantly affect the continuation of the trial
3. Violation of GCP, the trial protocol, or the contract impairing the appropriate conduct of the trial

The investigator / the trial site will be reimbursed for reasonable expenses incurred in case of trial termination (except in case of the third reason).

4. TREATMENTS

4.1 INVESTIGATIONAL TREATMENTS

Pramipexole SR 0.375 mg and 0.75 mg tablets, Pramipexole IR 0.25 mg and 1.0 mg tablets will be supplied by Boehringer Ingelheim.

4.1.1 Identity of the Investigational Medicinal Products

Table 4.1.1: 1 Test product 1: Pramipexole SR

Substance:	Pramipexole dihydrochloride monohydrate
Pharmaceutical formulation:	Tablets
Source:	Boehringer Ingelheim Pharma GmbH & Co KG, Germany
Unit strength:	0.375 mg and 0.75mg
Posology	0.375 mg, 0.75mg, 1.5mg, 2.25mg, 3.0mg, 3.75mg, or 4.5mg, once daily, at 7-9 pm before bedtime
Route of administration:	Oral (p.o.)

Table 4.1.1: 2 Test product 2: Pramipexole IR

Substance:	Pramipexole dihydrochloride monohydrate
Pharmaceutical formulation:	Tablets
Source:	Boehringer Ingelheim Pharma GmbH & Co KG, Germany
Unit strength:	0.25 mg and 1.0 mg
Posology	0.375 mg, 0.75mg, 1.5mg, 2.25mg, 3.0mg, 3.75mg, or 4.5mg, 3 times daily, the third dose at 7-9pm before bedtime
Route of administration:	Oral (p.o.).

4.1.2 Selection of doses in the trial

The dosing schedule for this study follows the standard doses for Pramipexole. Doses for this study used during the up-titration and the maintenance phase consist of the following seven dose levels:

Pramipexole SR 0.375 mg, 0.75 mg, 1.5 mg (0.75 mg*2), 2.25 mg (0.75 mg*3), 3.0 mg (0.75 mg *4), 3.75 mg (0.75 mg*5) or 4.5 mg (0.75 mg*6) at 7-9 pm before bedtime.

Pramipexole IR 0.375 mg (0.25mg*1/2 t.i.d.), 0.75 mg (0.25 mg t.i.d.), 1.5 mg (1.0mg*1/2 t.i.d.), 2.25 mg (1.0 mg *1/2 t.i.d. +1.0 mg *1/4mg t.i.d.), 3.0 mg (1.0 mg t.i.d.), 3.75 mg (1.0 mg t.i.d. + 1.0 mg *1/4mg t.i.d.), or 4.5 mg (1.0 mg t.i.d. + 1.0mg*1/2 t.i.d.)

During the 7-week up-titration phase, the need for up-titration will be assessed by the investigator at on-site visits and telephone contacts, based on efficacy (PGI-I) and tolerability. Between on-site visits, the investigator will contact the patient by phone call to check efficacy (PGI-I) and tolerability of the study treatment and, if necessary, decide if the dose level has to be up-titrated or down-titrated. The dose of study medication should be up titrated in all patients who are not at least “a little better” on the PGI-I. If the dose is not increased, the reason should be given by the investigator and recorded in the eCRF (e.g. dose not increased due to an Adverse Event). In case of dopaminergic side effects (dyskinesia, psychosis, etc.) during the up-titration phase, the investigator can reduce the level of the study medication to the previous dose level.

4.1.3 Method of assigning patients to treatment groups

After confirming that the patient meets all the eligibility criteria at Visit 2, the patient will be randomly assigned to SR or IR arm (with a randomization ratio of 1:1).

The randomization list will be carried out centrally using BI randomisation operator (ROP). Based on the randomization list, the external vendors will implement the assignment. The BI standard validated random number generating system will be used to generate the randomization list, which will be verified by an independent statistician who is not involved in the trial. The access to the randomization code will be supervised by the Clinical Trial Support Group. Any personnel directly involved in the conduct and analysis of the trial will have no access to the randomization schedule prior to the database lock.

The investigators will receive a manual describing how to communicate and implement the assignment with the support of the external vendor.

4.1.4 Drug assignment and administration of doses for each patient

The study consists of an 18-week, active treatment phase (up to a 7-week titration phase until optimal response, followed by an 11-week maintenance phase). At the end of the maintenance phase, patients who want to enter a down-titration phase, with a final visit to monitor tapering of the study medication. For other patients who want to maintain their

dosages, commercial Pramipexole IR/SR will be provided by themselves under the judgement of investigators.

Study site authorized personnel (registered in the investigator site file) will dispense the study medication during the on-site visits.

Pramipexole IR doses will be taken orally, in equally divided doses, three times per day with the third dose at 7-9 pm before bedtime, with a glass of water (approximately 150 mL) with or without food.

Pramipexole SR doses will be taken orally q.d. at 7-9 pm before bedtime. Each dose will be taken with a glass of water (approximately 150 mL) with or without food

Missed doses of IR will be skipped at any time.

Missed dose of SR should be taken within 12 hours after the regularly scheduled time. After 12 hours, the missed dose should be left out and the next dose should be taken on the following day at the next regularly scheduled time.

The dose level determined at the end of the titration phase will be maintained throughout the Maintenance Phase. Patients will use their last maintenance dose on the day of visit 7.

Patients who won't continue Pramipexole IR/SR treatment after trial completion will enter a down-titration phase on the day following Visit 7. Patients will take the taper medication during the week between visit 7 and follow-up visit 8. The medication dose will be reduced daily by one dose level. This tapering will take a maximum of six days (for patients treated with the highest dose level of 4.5 mg per day during the maintenance phase). Patients will return for a follow-up visit (visit 8) at last study dose + 2 days after visit 7 (at least 48 hours after the last study drug intake in the down titration phase).

Commercial Pramipexole IR/SR is allowed to be prescribed to patients at visit 7 in the judgement by investigators and patients. In this case, taper process is not applicable to those patients. However, all other procedures at visit 7 and visit 8 will be performed as no major changes, except for compliance check of taper medication.

4.1.5 Blinding and procedures for unblinding

4.1.5.1 Blinding

There will be no blinding as discussed in [Section 3.2](#).

4.1.5.2 Unblinding and breaking the code

Not applicable.

4.1.6 Packaging, labelling, and re-supply

The investigational products will be provided by BI. For details of packaging and the description of the label, refer to the ISF.

IMPs will be packaged and labelled in accordance with the principles of Good Manufacturing Practice (GMP). Trial drug packages will have unique medication numbers which will be used for tracking purposes only. The medication numbers will not be linked to randomisation numbers.

Pramipexole SR will be supplied as film-coated tablets. Available dosage strength will be 0.375 mg and 0.75 mg. Tablets will be supplied in Aluminium-aluminium blister sealed with Aluminium plastic plate containing 10 tablets.

Pramipexole IR will be supplied as film-coated tablets. Available dosage strength will be 0.25 mg and 1.00 mg. Tablets will be supplied in Aluminium-aluminium blister sealed with Aluminium plastic plate containing 30 tablets.

Re-supply to the sites will be managed as manually. Study site authorized personnel and Clinical Research Associate (CRA) will monitor the IMP number in site and inform Clinical Trial Manager (CTM) for re-supply if the IMPs are inadequate.

4.1.7 Storage conditions

Trial medication, which will be provided by the sponsor, must be kept in a secure, limited access storage area under the storage conditions defined below until supplied/administered to patient. Temperature logs must be maintained to make certain that the drug supplies are stored at the correct temperature. In case temperature would be out of range, this has to be managed based on STORM document in ISF

Only authorized personnel as documented in the <Trial Staff List> form in the ISF may dispense medication to trial subjects. Receipt, usage and return of the trial medication must be documented on the respective forms in the ISF.

4.1.7.1 Storage conditions for IR

Store sealed below 30°C (86°F), away from light. Keep out of the reach of children.

4.1.7.2 Storage conditions for SR

Pramipexole SR must be store sealed in the room temperature. Keep out of the reach of children.

4.1.8 Drug accountability

The investigator and/or pharmacist and/or investigational drug storage manager will receive the investigational drugs delivered by the sponsor when the following requirements are fulfilled:

- Approval of the clinical trial protocol by the Institutional Review Board (IRB) / ethics committee,
- Availability of a signed and dated clinical trial contract between the sponsor and the investigational site,
- Approval/notification of the regulatory authority, e.g. competent authority,

- Availability of the curriculum vitae of the Principal Investigator,
- Availability of a signed and dated clinical trial protocol,

Investigational drugs are not allowed to be used outside the context of this protocol. They must not be forwarded to other investigators or clinics. The patients will be instructed to return to the study site all dispensed blister packs at each on-site visit, including unused and partially used study medication. The unused and partially used study medication will be returned to patients for treatment after drug accountability until the end of treatment. The investigator and/or pharmacist and/or investigational drug storage manager must maintain records of the product's delivery to the trial site, the inventory at the site, the use by each patient, and the return to the sponsor or warehouse / drug distribution centre or alternative disposal of unused products. If applicable, the sponsor or warehouse / drug distribution centre will maintain records of the disposal.

These records will include dates, quantities, batch / serial numbers, expiry ('use-by') dates. The investigator / pharmacist / investigational drug storage manager will maintain records that document adequately that the patients were provided the doses specified by the Clinical Trial Protocol (CTP) and reconcile all investigational products received from the sponsor. At the time of return to the sponsor and/or appointed Contract Research Organisation (CRO), the investigator / pharmacist / investigational drug storage manager must verify that all unused or partially used drug supplies have been returned by the clinical trial patient and that no remaining supplies are in the investigator's possession.

4.2 OTHER TREATMENTS, EMERGENCY PROCEDURES, RESTRICTIONS

4.2.1 Other treatments and emergency procedures

- **L-Dopa⁺ treatment:**

At study entry, patients must be treated with L-Dopa⁺ (i.e. standard and/or sustained release Levodopa/DDC inhibitor), or with a combination of L-Dopa⁺ and entacapone, at an optimized dose according to investigator's judgment, this dose being stable for at least 4 weeks prior to visit 2. While patients have to be on a stable dose of L-Dopa⁺ prior visit 2 for at least 4 weeks, it is possible that the L-Dopa⁺ dose may need to be adjusted with the addition of Pramipexole (SR or IR) during the trial.

- **Other Parkinson's disease treatments:**

A concomitant treatment with one or more of the following drugs will be allowed (at a stable dose for at least 4 weeks prior to randomization visit and the investigator does not intend to change this treatment during the treatment phase):

- Anti-parkinsonian anticholinergics;
- And/or selegiline, rasagiline, or other MAO-B-Inhibitor;
- And/or amantadine;
- And/or entacapone (or other COMT-Inhibitor).

The above list may not be exhaustive. In case another treatment is taken by the patient for his PD, a previous agreement should be given by the CTM before the patient can be enrolled in the trial.

Patients must not have been treated with sustained release dopaminergic drug (i.e. sustained release Levodopa/DDC inhibitor) after supper, or any anti-PD medication after 9 pm within 4 weeks prior to randomization visit.

The timing of administration as well as the doses of these treatments will have to remain stable during the treatment phase.

- **Other concomitant treatments:**

Other concomitant therapies that are not listed as restrictions will be allowed at the discretion of the investigator or sub-investigator. They should be limited to therapies essential for the care of the patient. The reason for use will be documented in the e-CRF.

- **Rescue medication**

There is no established antidote for overdose of a dopamine agonist. If signs of central nervous system stimulation are present, a neuroleptic agent may be indicated. Management of the overdose may require general supportive measures along with gastric lavage, intravenous fluids, and electrocardiogram monitoring. Haemodialysis has not been shown to be helpful.

4.2.2 Restrictions

4.2.2.1 Restrictions regarding concomitant treatment

The administration of any other dopamine agonists with the study medication will necessitate termination of the patient's participation in this study.

The following therapies must not be taken for the specified times prior to visit 2 and during the treatment phase:

- Dopamine agonist (including Pramipexole): at least 4 weeks,
- Any hypnotic medication (i.e. diazepam, clonazepam, estazolam, alprazolam, zolpidem, etc.): at least 4 weeks,
- Any medication with central dopaminergic antagonist activity (i.e. typical neuroleptics, atypical antipsychotics, reserpine, methyl dopa, centrally-active antiemetics, etc.): at least 4 weeks,
- Flunarizine: at least 3 months,
- Methylphenidate: at least 4 weeks,
- Cinnarizine: at least 4 weeks,
- Amphetamines: at least 4 weeks,
- Any other investigational drugs: at least one month or five-times the half-life of the investigational drug (whichever is longer).

A previous treatment with Pramipexole IR/SR is allowed 4 weeks before visit 2, provided the treatment was not discontinued due to a serious/clinically significant drug related Adverse Event, according to investigator's judgement.

The above list is not exhaustive. If the investigator has used or if he/she intends to use similar drugs not specified above, he/she should contact the sponsor to confirm patient's participation to the trial / continuation in the trial.

4.2.2.2 Restrictions on diet and life style

Since somnolence is a frequent adverse event with potentially serious consequences, patients should neither drive a car nor engage in other potentially dangerous activities until they have gained sufficient experience with SIFROL® sustained release tablets and SIFROL® immediate release tablets to gauge whether or not it affects their mental and/or motor performance adversely.

4.2.2.3 Restrictions regarding women of childbearing potential

Women of childbearing potential must use the contraception methods described in the patient information.

4.3 TREATMENT COMPLIANCE

Patients are requested to bring all remaining trial medication including the empty package material with them at each visit. The investigator will be responsible for the assessment of patient compliance with study medication at each visit, by physical count of returned study medication. This information will be recorded and retained in the patient's record. Percent compliance will be calculated based on dose in mg.

Medication compliance should be between 80-120% inclusive, at every visit. Isolated episodes of compliance should be evaluated on a case-by-case basis, before arbitrary discontinuation of a patient for non-compliance. The investigator will be encouraged to counsel patients on the importance of taking study medication as directed at each visit. For trial evaluation, handling of non-compliant patients will be described in the Trial Statistical Analysis Plan (TSAP). Decisions regarding patient eligibility due to poor compliance will finally be determined at Blinded Report Planning Meetings (BRPM), which will occur prior to locking of the database.

5. ASSESSMENTS

5.1 ASSESSMENT OF EFFICACY

Refer to [flow-chart](#) and to [Section 6](#) for a detailed time schedule for measurements.

Data analysis specifications for the observations mentioned below will be described in the statistical section ([Section 7](#)) or the TSAP.

Parkinson's disease Sleep Scale 2nd version (PDSS-2) [R04-0948]

The PDSS-2 consists of 15 questions about various sleep and nocturnal disturbances which are to be rated by the patients using one of five categories, from 0 (never) to 4 (very often). Patients will be asked to rate the severity of each question based on their experience during the past week (7 days) from 0 (Never) to 4 (Very often, that means 6 to 7 days a week). PDSS-2 total score ranges from 0 (no disturbance) to 60 (maximum nocturnal disturbance). There are three sub-scales from the three-factor solution, one comprising nocturnal movement-related problems (factor 1: "motor problems at night"), a second describing the disease specific symptoms (factor 2: "PD symptoms at night") and the third representing sleep specific disturbances (factor 3: "disturbed sleep"). A total score of ≥ 18 defines clinically relevant PD-specific sleep disturbances. According to previous study, any improvements in PDSS-2 less than -3.44 points can represent clinically important changes for the patients. That is to say, a minimal clinically important difference (MCID) of PDSS-2 [R17-4026] is -3.44 points.

Nocturnal Hypokinesia Questionnaire (NHQ)

The Nocturnal Hypokinesia Questionnaire is designed to assess hypokinesia symptoms in night in PD patients, composed of two sections. Section 1 is assessed by PD patients. There are four domains in section 1 to assess "turning over in bed", "getting out of bed", "parkinsonian motor symptoms" and "others" separately. The domains in section 2 are the same with it in section 1. Section 2 is assessed by spouses or caregivers who are with the patients during the night.

SCOPA-Sleep [R08-5312]

The SCOPA-Sleep is a short, self-rating scale designed to evaluate nocturnal sleep quality and daytime sleepiness in patients with PD. It is composed of three parts: a nighttime scale (NS), a single-item about perceived quality of nocturnal sleep, and a daytime sleepiness scale (DS) that includes an item about unexpected onset of sleep.

The NS is a five-item scale with four response options (0-not at all to 3-very much) that addresses nighttime disturbances that "occurred in the previous month". The five items include sleep initiation, sleep fragmentation, sleep efficiency, sleep duration, and early wakening. Total NS score runs from 0 to 15, with higher scores reflecting more severe problems. The additional "quality of sleep" question assesses the overall nighttime sleep quality on a seven-point scale (ranging from slept very well to slept very badly). This item is not included in the total NS score. The DS subscale evaluates daytime sleepiness, also in the past month, and includes six items with four response options, from 0 (never) to 3 (often), and a maximum total score of 18. These DS items are addressed to how often the patient fell

asleep unexpectedly, but in particular situations (while sitting quietly, watching TV or reading, talking to someone), had difficulty to remain awake, and self-perception of daytime sleepiness as a problem.

Early Morning Off (EMO) [P17-11335]

The EMO is measured by the question of “do you feel like your bodily movements are poor when you wake up?” Patients will answer this question according to frequency during the past one week by scoring from 0 (“never”) to 4 (“very often” or “6 to 7 days a week”). EMO score should be rated before the first anti-PD drug taking in early morning, and within half an hour after waking up. The responder of EMO is the patient improved at least 1 comparing to his/her baseline condition.

Parkinson's disease Questionnaire (PDQ) -8 [R04-4222]

The PDQ-39 is a self-administered, disease specific measure of health status which covers eight dimensions of ill-health, and contains 39 questions. The 8 domains include:

- Mobility (e.g. fear of falling when walking): 10 items,
- Activities of daily living (e.g. difficulty cutting food): 6 items,
- Emotional well-being (e.g. feelings of isolation): 6 items,
- Stigma (e.g. social embarrassment): 4 items,
- Social support: 3 items,
- Cognition: 4 items,
- Communication: 3 items,
- Bodily discomfort: 3 items.

The PDQ-8, an 8 item self-report questionnaire derived from PDQ-39. Each item selected is the one most highly correlated with the overall domain score to which it contributes. The items were summed together and transformed onto a score from 0 to 100. The PDQ-8 has been shown to exhibit appropriate levels of reliability, validity and responsiveness.

Clinical Global Impression of Improvement (CGI-I) [R96-0188];

The CGI was developed by the Early Clinical Drug Evaluation Unit (ECDEU) of the National Institute of Mental Health as an independent, simple way for clinicians to make overall evaluations of a patient's central nervous system (CNS) disease status. The ratings were used initially in outpatients with various psychiatric disorders. The CGI-I will be rated (from 1: very much improved, to 7: very much worse) by the same evaluator to assess the overall status of Parkinson's disease, after interviewing the patient about the various aspects of the PD and after evaluating AE and concomitant treatments. The evaluator will complete the scale by comparing the patients' status during the past week to their baseline condition. The responder of CGI-I is the patient rated of any improvement (1 = Very much better, 2 = Much better, or 3 = A little better).

Patient Global Impression of Improvement (PGI-I) [R96-0188];

The PGI-I scale is a patient-rated instrument which will be used to measure the improvement (from 1: very much better, to 7: very much worse) of the patient's Parkinson disease symptoms throughout the study. Patients will complete the scale by comparing their status during the past week to their baseline condition. The responder of PGI-I is the patient rated of any improvement (1 = Very much better, 2 = Much better, or 3 = A little better).

Epworth Sleepiness Scale (ESS) [[R97-0791](#)];

The ESS is a patient-rated scale about how likely one is to fall asleep during situations as passive and inconsequential as “watching TV” to as active as “sitting and talking to someone” and as consequential as “in a car, while stopped for a few minutes in traffic.” “Chance of dozing” is rated as an integer from 0 (no chance) to 3 (high).

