2.1.3 Secondary endpoint(s)

Secondary efficacy endpoints are (to be assessed at week 18):

- Nocturnal Hypokinesia Questionnaire (NHQ) score (change from baseline);
- SCOPA-Sleep score (change from baseline);
- Early Morning Off (EMO) score (change from baseline);
- Responder rate for PDSS-2 total score < 18;
- Responder rate for EMO score;
- The Parkinson's disease Questionnaire (PDQ)-8 score (change from baseline);
- Responder rate for Clinical Global Impression of Improvement (CGI-I);
- Responder rate for Patient Global Impression of Improvement (PGI-I);
- Epworth Sleepiness Scale (ESS) score (change from baseline).

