6.2.2.2 Up-titration phase

Patients will have weekly contact to the study site during the up-titration phase either as office visits or telephone calls. The complete seven weeks of up-titration are used to safely increase the study medications to the highest tolerated optimal dose for effective response. The investigator should use his/her clinical judgment in adjusting the dose to a dose where clinical improvement is reached. Furthermore, if a patient is unable to tolerate an increased dose level, the medication can be lowered one level.

It is possible that the L-Dopa⁺ dose may need to be adjusted with the addition of Pramipexole (SR or IR) during the up-titration Phase.

Visit 3 (i.e., week 2) at day 14 ± 2:

- Obtain vital signs (blood pressure, pulse) and weight
 - Check for abnormal behavior. The MMIDI sub-scale has to be completed if the patient experiences any abnormal behavior
 - Ask patient to score the severity of EMO
 - Ask patient to complete the ESS
 - Ask patient to complete the PDSS-2
 - Ask patient to complete the NHQ Section 1. NHQ Section 2 should be completed by spouses or caregivers who are with the patients during the night at the same day. If no spouses or caregivers during the night, document it in the medical note and no need to complete NHQ Section 2.
 - Ask patient to complete the SCOPA-Sleep
 - Ask patient to complete the PGI-I questionnaire
 - Perform medication compliance check
 - Review concomitant therapies including PD therapies
 - Record AEs or follow-up on AEs continuing from a prior visit
 - Dispense study medication to the patient to ensure the sufficient study medication until the next on-site visit with verbal instructions on how to take the medication. Remind the patient to take the study medication Pramipexole IR regularly three times per day with the third dose at 7-9 pm before bedtime or take study medication Pramipexole SR once daily at 7- 9 pm before bedtime. Additionally, remind the patient to bring the medication boxes (including all blank blister(s), unused and partially used study medication) back at the next scheduled on-site visit. The unused and partially used study medication will be returned to patients for treatment after drug accountability until the end of treatment.
-
- Schedule patient's next contact (telephone call, TC2) to study site one week later

Visit 4 (i.e., week 4) at day 28 ± 2:

- Obtain vital signs (blood pressure, pulse) and weight

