Interim telephone calls will be performed in order to avoid weekly on-site visits for the patients. If for some instance a patient will not have telephone access at home, the patient could perform a clinic visit. These unscheduled visits need to be reported then formally as TC's with a remark in the comments section of the corresponding eCRF page.

In the telephone calls the following information needs to be obtained:

- Check medication compliance
- Ask patient to complete the PGI-I questionnaire (the value will be recorded in the eCRF)
- Review concomitant therapies including PD therapies
- Record AEs or follow-up on AEs continuing from a prior visit. Evaluate patient's response to current dose level. If warranted, increase to next dose level. If patient is

already at optimal dose level, instruct patient to continue with the same dose level. If patient experienced side effects, the dose level can be adjusted to the next lower dose level.

- Schedule patient's next on-site visit.

TC5 will be the last time when the investigator can decide to down-titrate or to up-titrate the study medication. From TC3 to TC5, if pramipexole dose should be adjusted due to unsatisfactory efficacy or adverse event, on-site visit should be added to adjust dose.

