7.2 NULL AND ALTERNATIVE HYPOTHESES

For pilot stage I, there is no (confirmatory) hypothesis testing foreseen in a strict statistical sense. Analyses are descriptive in nature including two-sided p-values and confidence intervals throughout from statistical models used for explorative purposes.

For stage II, the assumption of the hypothesis testing will be based on the results of pilot stage I, which will be added once the topline results of stage I are worked out.

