7.3.2 Secondary endpoint analyses

For continuous endpoints, the same method as the primary analysis will be used. For responder rates, logistic regression analyses will be performed with treatment and baseline (if baseline was measured) as the independent variables.

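### Does using the same PGI-I category as up-titration trigger and responder cut spoil the PGI-I responder comparison?

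*Protocol*

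**What the plan says.** Section 5.1 fixes the cut: "The responder of PGI-I is the patient rated of any improvement", meaning ratings 1 to 3 on the seven-point scale, where 3 is *a little better*.

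Section 4.1.2 fixes the trigger: "The dose of study medication should be up titrated in all patients who are not at least" *a little better* on the PGI-I. The flow chart schedules the PGI-I at all seven titration contacts, weeks 1 to 7. Section 4.1.4 then says: "The dose level determined at the end of the titration phase will be maintained throughout the Maintenance Phase".

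The titration target is wider than the trigger. Section 6.2.2.2 aims at the "highest tolerated optimal dose for effective response", and the synopsis asks in both arms for the greatest therapeutic effect without intolerable side effects.

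Section 2.1.3 lists the PGI-I responder rate at week 18 among nine secondary efficacy endpoints. Section 7.3.2 gives the model: "For responder rates, logistic regression analyses will be performed with treatment and baseline (if baseline was measured) as the independent variables". Section 7.2 says of Stage I: "Analyses are descriptive in nature including two-sided p-values and confidence intervals".

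**The concern.** The rating that steers the dose is later cut at the steering threshold and compared between arms. If SR worked better than IR, IR patients could be titrated further until they too rated themselves *a little better*. The responder rates would converge and the difference would sit in the dose, where the responder model does not look. The cut also discards the seven-category rating that is already recorded. A result of no difference in PGI-I responders might then be taken for equal effect when one arm needed more drug to get there.

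**Working it through.** **The plan's own figures.** The protocol states no PGI-I rate, effect or dose response. Section 7.7 gives probabilities for PDSS-2 only, and they reproduce. With SD 8 and N = 80 the standard error is 8 × √(4/80) = 1.789. For a true difference of −4.00, Φ((−3.44 + 4.00)/1.789) = Φ(0.313) = 62.3%. For −5.00, Φ(1.56/1.789) = Φ(0.872) = 80.8%. These figures say nothing about PGI-I. They only supply a scale: 4.00/8 = 0.5 SD, borrowed below as an assumed shift.

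**Validity.** Both arms follow the same trigger. If the formulations do not differ, dose paths and responder rates have the same distribution in both arms. In simulation with titration and no shift, the yes/no test rejects in 4.5 to 6.0% of trials at a nominal 5%. The overlap creates no bias towards either arm.

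**Is the ordinal advantage caused by titration?** Assumptions: 40 per arm, two-sided 0.05, a normal latent scale, and a Wilcoxon test with categories 5 to 7 pooled against a two-proportion z test. Without titration, IR response is set at 50, 70, 85 or 90%. With titration there are 12 settings: starting response 50 or 30%; gain per dose step 0.1, 0.3 or 0.5 SD; goal *a little better* or *much better*. Gain is ordinal minus yes/no power.

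| Shift | Gain without titration (50, 70, 85, 90%) | Gain with titration |
|---|---|---|
| 0.25 SD | 18.1−15.6 = 2.5; 17.9−12.8 = 5.1; 17.5−11.1 = 6.4; 17.4−10.2 = 7.2 | 0.3 to 4.2 |
| 0.5 SD | 55.3−42.4 = 12.9; 55.2−35.6 = 19.6; 53.5−26.5 = 27.0; 53.2−20.7 = 32.5 | 5.3 to 15.6 |
| 0.75 SD | 88.0−73.1 = 14.9; 87.7−62.6 = 25.1; 87.0−45.9 = 41.1; 86.0−32.6 = 53.4 | 11.4 to 31.9 |

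The gain is there without titration, over a higher range at each shift. It is the usual loss from dichotomising, not a product of the shared category.

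**What does the shared category itself do?** Comparing titration with no titration does not answer this, because any effective titration raises response rates and so lowers the power of a yes/no test. The relevant contrast is titration to *a little better* against titration to the tolerated maximum without regard to PGI-I. Yes/no power at a shift of 0.5 SD:

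| Starting response | Gain per dose step | PGI-I goal | Tolerance only | Difference |
|---|---|---|---|---|
| 50% | 0.1 SD | 34% | 36% | −2 |
| 50% | 0.3 SD | 19% | 23% | −4 |
| 50% | 0.5 SD | 12% | 7% | +5 |
| 30% | 0.1 SD | 41% | 43% | −2 |
| 30% | 0.3 SD | 24% | 29% | −5 |
| 30% | 0.5 SD | 14% | 19% | −5 |

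At 0.25 SD the difference is about −3 to +2 points.

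**Does the effect move into the dose?** That depends on the assumed goal. With the *a little better* goal, 50% starting response and 0.5 SD per step, a 0.5 SD shift gives mean dose levels of 2.60 (IR) and 2.02 (SR), and a comparison of dose levels has 60.4% power. With the tolerance-only goal and tolerated maxima spread evenly over levels 3 to 7, both arms average (3+4+5+6+7)/5 = 5.0, and the dose comparison rejects in about 5% of trials, its false-positive rate. The synopsis and Section 6.2.2.2 describe a goal beyond the trigger, so the first case is the extreme one.

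**The case for a change.** The strongest point for the concern is that its facts are exact and need no assumption: one scale, one boundary, both arms, and the dose reached is then held. The cut, trigger, endpoint and model are all fixed in the protocol. Section 3.3 also lets another endpoint that shows great benefit of SR become primary in Stage II, so secondary endpoints can carry some weight.

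Part of this stands. Where patients are titrated only until the trigger is met, some of a true difference does move into the dose, and a null responder result on its own would not show equal effect. But the protocol draws no such conclusion. The PDSS-2 result drives Table 3.3:1, and the Section 3.3 route needs a large positive signal on another endpoint, not a null one. With 40 per arm and a 0.25 SD shift, the yes/no test has only 10.2 to 15.6% power even without titration, so a null result says little in any case.

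The protocol's background also gives no reason to expect a large dose difference. Section 1.2 reports equivalent 24-hour exposure. Section 1.4 reports similar mean daily dose and dose distribution for SR and IR, though in early disease. The PGI-I rates Parkinson symptoms overall, so the 0.5 SD borrowed from a sleep scale may be generous.

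**Conclusion.** The concern does not hold. Nothing is misstated or contradictory, and the planned logistic regression of PGI-I response is a valid comparison of the arms as treated. The shared category changes its power by at most about 5 points either way in the settings examined. These rest on assumed response rates, dose effects and tolerability, because the protocol gives none.

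What remains is a wish for supportive output: an ordinal analysis and a table of dose by arm. Both could be informative, but they replace no stated analysis. Sections 5.1 and 7 leave such detail to the statistical analysis plan, which is not at hand. The published text also passes from Section 7.3.2 to 7.3.4, so their absence cannot be asserted.
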